IMV	Institut für Medizinische Virologie in Zürich
ISO	International Organisation for Standardisation
ITT	Intention to treat
MD	Medical Device
MedDO	Medical Device Ordinance (in German: MepV, in French: ODim)

PI	Principal Investigator
RBD	Receptor binding domain
RECORD	REporting of studies Conducted using Observational Routinely-collected Data
SARS-CoV-2	Severe acute respiratory syndrome coronavirus 2
SDV	Source Data Verification
SHCS	Swiss HIV Cohort Study
SOP	Standard Operating Procedure
SPC	Summary of product characteristics
SPIRIT	Standard Protocol Items: Recommendations for Interventional Trials
STCS	Swiss Transplant Cohort Study
SUSAR	Suspected Unexpected Serious Adverse Reaction
TMF	Trial Master File

STUDY SYNOPSIS

Controlled trials to assess approved SARS-CoV-2 vaccines in immunocompromised patients: Third sub-protocol for an observational study comparing benefits and potential risks of the newly approved bivalent SARS-CoV-2 vaccines

Brief Title: Immunocompromised Swiss Cohorts Based Trial Platform, Acronym: COVERALL (COrona VaccinE tRiAL pLatform) bivalent

Rationale: Since January 12, 2021 two mRNA based vaccines against SARS-CoV-2 by Pfizer-BioNTech (Comirnaty®) and by Moderna (COVID-19 mRNA Vaccine Moderna®) have been licensed in Switzerland and roll-out of vaccines has started.

We have set up a COrona VaccinE tRiAL pLatform (COVERALL) nested into the existing prospectively collected data structure of the Swiss HIV Cohort Study (SHCS) and the Swiss Transplant Cohort Study (STCS). Within the frame of a first sub-study (see first sub-protocol) we have assessed in a head-to-head comparison the efficacy of BNT162b2 by Pfizer-BioNTech and mRNA-1273 by Moderna in immunocompromised patients form the SHCS and the STCS. In these patients the antibody response of mRNA-1273 was non-inferior to BNT162b2. Patients living with HIV had in general an antibody response, while a high proportion of transplant recipients had no antibody response. The second substudy found similar results 8 weeks after the 3rd vaccination (i.e. non-inferiority of moderna vaccine; antibody response).

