Since our trial platform is nested within two national cohort studies (SHCS and STCS), we have the possibility to identify and invite cohort patients who will receive the new bivalent mRNA Sars-CoV-2 vaccine in the frame of clinical routine. We plan to enrol the following number of individuals:

Scenario 1:

160 patients receiving bivalent (Wuhan/BA.1) SARS-CoV-2 mRNA-1273.214 vaccine by Moderna

- kidney transplant recipients (n=30)
- lung transplant recipients (n=30)
- people living with HIV with CD4 cell counts below 350 cells/ μ L (n=50)
- people living with HIV with CD4 cell counts of \geq 350 cells/µL (n=50)

AND

80 patients receiving bivalent (Wuhan/BA.1) SARS-CoV-2 mRNA vaccine by Pfizer-BioNTech

- kidney transplant recipients (n=10)
- lung transplant recipients (n=10)
- people living with HIV with CD4 cell counts below 350 cells/µL (n=30)
- people living with HIV with CD4 cell counts of \geq 350 cells/µL (n=30)

Sub-sample: A sub-sample of 60 patients will be selected (n=40 bivalent mRNA-1273.214 vaccine by Moderna; n=20 bivalent SARS-CoV-2 mRNA vaccine by Pfizer-BioNTech) for whom we will assess the T-Cell response, measured using the Quant-T-Cell SARS-CoV-2 by Euroimmun and Elecsys® IGRA SARS-CoV-2 by Roche. For this sub-sample we aim to prioritize patients which are at higher risk for a low immune response (i.e. solid organ transplant recipients and people living with HIV wit CD4 counts below 350 cells/µL so that we can include from each of the above groups 10 patients who received bivalent mRNA-1273.214 and 5 who received bivalent SARS-CoV-2 mRNA vaccine by Pfizer-BioNTech).

Scenario 2:

160 patients receiving bivalent (Wuhan/BA.1) SARS-CoV-2 mRNA-1273.214 vaccine by Moderna

- kidney transplant recipients (n=30)
- lung transplant recipients (n=30)
- people living with HIV with CD4 cell counts below 350 cells/µL (n=50)
- people living with HIV with CD4 cell counts of \geq 350 cells/µL (n=50)

Sub-sample: A sub-sample of 40 patients will be selected for whom we will assess the T-Cell response (10 from each of the groups listed above).

Biological Sample and health related data Collection and Duration:

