7.6 ASSIGNMENT TO STUDY GROUPS

Since this is an observational study extension, we will not do any active assignment. Participants will receive the bivalent vaccine which they are given during routine practice. We will implement monitoring reports so capture how many patients from which sub-group are already participating. When the required sample size is reached for a specific sub-group investigators will be informed to stop recruitment for this sub-group of patients.

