10.1 ASSESSMENTS OF OUTCOMES

10.1.1 Assessment of immunological endpoints

We will assess the proportion of patients with a positive antibody response to SARS-CoV-2 spike (S1) protein receptor binding domain in human serum or plasma assessed by the commercial immunoassay Elecsys Anti-SARS-CoV-2 S (Elecsys S) from Roche (1) 4 weeks, 8 weeks, and 6 months after vaccination. An antibody response will be considered to be still sufficient, using the threshold \geq 100 units/ml, predicting a protective immune response as indicated by Hall et al. (2), and Khoury and colleagues (3). We will also assess antibody response at baseline (i.e. before vaccination with bivalent SARS-CoV-2 vaccine). However, we assume that some patients may have received already the bivalent SARS-CoV-2 vaccine before the start of this study, hence we will not have a baseline blood sample from those patients. Furthermore we will measure the geometric mean of quantitative antibodies against RBD at 4 weeks, 8 weeks, and 6 months using Elecsys S test from Roche and the proportion of patients with a positive antibody response using SARS-CoV-2 spike (S1) Elecsys S by Roche, using a threshold of \geq 0.8 units/ml as defined by the manufacturer at 4 weeks, 8 weeks, and 6 months.

Therefore, a blood sample will be taken during each study visit (EDTA blood sample (1 x 3 ml)):

Participating centres can decide if they want to conduct Elecsys® Anti-SARS-CoV-2 N and S tests locally at their own routine laboratory, or if they want to send the blood samples in large batches for the analyses to the Institut für Medizinische Virologie (IMV), in Zürich

In a sub-sample of 40 patients who receive the bivalent mRNA SARS-CoV-2 vaccine from Moderna and 20 who receive bivalent vaccine from Pfizer-BioNTech, we will assess the T-Cell response using a commercially available IFN- γ release assay (Quant-T-Cell test by Euroimmun (19)) at baseline, 4 weeks and 6 months. We will use the same blood sample to conduct an additional T-Cell test by Roche (Elecsys® IGRA SARS-CoV-2 (20)) to compare the performance of the two diagnostic tests.

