13. STATISTICAL METHODS

Hypothesis

All analysese conducted will be of exploratory nature. For scenario 1, we expect to observe similar immunological outcomes for the two bivalent vaccines in our study population.

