13.3.2 Analyses of immunological and clinical outcomes

Descriptive statistics will be used to present immunological and safety outcomes. We will report frequency and percentage with 95% Wald confidene interval (CI) of positive immune response and

geometric mean titer (GMT) with 95% CI. GMT are defiened as the anit-logs of the means and addressed anticipated right-skewness of the data. Safety outcomes will be reported as frequency and percentage with 95% CI. For scenario 1, we will additionally report mean difference in positive response and ratio of GMT between the two bivalent vaccines with 95% CI.

Baseline and demographic characteristics will be summarised overall and -for scenario 1 – by vaccine received.

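### The Scenario 1 vaccine comparison is not stratified by patient group, although the recruitment targets put 37.5% transplant recipients in one arm and 25% in the other

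*Protocol*

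**What the plan says.** The Protocol (third sub-protocol) plans descriptive statistics for the antibody endpoints in section 13.3.2, and adds one between-vaccine analysis: "For scenario 1, we will additionally report mean difference in positive response and ratio of GMT between the two bivalent vaccines with 95% CI". It names no stratification, covariate adjustment or weighting, and no reporting of outcomes by patient group. Only baseline and demographic characteristics are to be summarised by vaccine. Section 7.2.3, on other methods of minimising bias, has no text in the supplied copy.

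The Synopsis (Number of Participants enrolled) sets the Scenario 1 targets: "160 patients receiving bivalent (Wuhan/BA.1) SARS-CoV-2 mRNA-1273.214 vaccine by Moderna" and "80 patients receiving bivalent (Wuhan/BA.1) SARS-CoV-2 mRNA vaccine by Pfizer-BioNTech", each divided into four groups (kidney transplant, lung transplant, HIV with CD4 below 350, HIV with CD4 of 350 or more). Section 7.6 applies the targets as caps: "When the required sample size is reached for a specific sub-group investigators will be informed to stop recruitment for this sub-group of patients".

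On earlier vaccine doses, the Synopsis and section 4.1 report: "Patients living with HIV had in general an antibody response, while a high proportion of transplant recipients had no antibody response". They describe the results after the third dose as similar.

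The comparison is called non-randomised in the Synopsis and section 4.1, and section 13 states "All analysese conducted will be of exploratory nature".

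**The concern.** Comparing the two vaccines is the stated Scenario 1 objective (section 6.1). A difference or GMT ratio taken across whole arms mixes two contrasts: vaccine against vaccine, and HIV against transplant. The second enters because the targets fix different patient mixes in the two arms, so the imbalance is written into the design and is not a chance event.

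The protocol discusses comparability of the arms only in relation to time (the three-month limit on opening the second arm), not patient mix. The first sub-protocol did not have this problem: its randomisation used minimisation within each cohort separately (section 6.1 of the Combined protocol and SAP), which keeps the cohort mix similar between arms.

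At stake is the headline comparison. The protocol expects similar outcomes for the two vaccines, and a reader could take a case-mix artefact as evidence against that.

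**Working it through.** **Inputs from the documents.** Moderna: kidney 30, lung 30, HIV 50 + 50. Pfizer-BioNTech: kidney 10, lung 10, HIV 30 + 30. The sums are 160 and 80, total 240, which reproduces the sample size in section 13.1.

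**Mix.** Transplant share is 60/160 = 0.375 versus 20/80 = 0.25, a gap of 0.125. Kidney to lung and low to high CD4 are both 1:1 in each arm, so the only built-in imbalance is HIV versus transplant.

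**Inputs that are assumptions.** The documents give no response rates or titres by group, so a range is shown.

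**Difference in positive response.** With identical vaccines in every group, the expected crude difference (Moderna minus Pfizer-BioNTech) is

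-0.125 × (HIV rate - transplant rate).

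For example, at 97/70% the arm rates are 0.625 × 97 + 0.375 × 70 = 86.9% and 0.75 × 97 + 0.25 × 70 = 90.2%, a difference of -3.4 points. Interval half-width and coverage come from simulation with fixed targets and Wald intervals (400,000 runs). The Mantel-Haenszel (MH) columns use the same runs, stratified by the four groups with the Sato variance.

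| Assumed HIV/transplant response | Spurious difference (points) | Crude half-width | Crude coverage | MH mean difference | MH coverage |
|---|---|---|---|---|---|
| 98/90% | -1.0 | 5.4 | 90% | 0.0 | 93% |
| 98/80% | -2.3 | 6.9 | 88% | 0.0 | 94% |
| 97/70% | -3.4 | 8.3 | 87% | 0.0 | 94.5% |
| 98/50% | -6.0 | 9.8 | 80% | 0.0 | 95% |

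In the first row part of the loss is not due to mix: with 37.5% transplant recipients in both arms, the Wald interval still covers only 93.7%, so mix accounts for about 4 points.

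**GMT ratio.** The expected crude ratio is 10^(-0.125 × log10 of the HIV:transplant titre ratio). Coverage is simulated (60,000 runs, Welch intervals, assumed within-group SD of 0.5 and 0.7 log10).

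| Assumed HIV:transplant titre ratio | Expected ratio (truth 1.00) | Crude coverage, SD 0.5 / 0.7 |
|---|---|---|
| 2 | 0.92 | 93% / 94% |
| 5 | 0.82 | 85% / 89% |
| 10 | 0.75 | 80% / 85% |
| 30 | 0.65 | 72% / 78% |
| 100 | 0.56 | 66% / 73% |

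A linear model adjusted for group gives a ratio of 1.00 with coverage of about 95% throughout.

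**Sensitivity to the achieved mix.** The targets may not be met exactly. At 97/70%, with Moderna at 37.5%, a Pfizer-BioNTech transplant share of 20%, 25% or 30% gives -(0.375 - share) × 27 = -4.7, -3.4 or -2.0 points.

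**The case against.** The strongest reply is that this is a descriptive, exploratory, openly non-randomised contrast with no test, margin or decision rule. For proportions the shift is smaller than the half-width of a single study's interval, and the baseline table by vaccine would probably reveal the mix. All of this is fair and limits the harm. It does not justify an estimate with a known direction of bias when the cause is the plan's own targets. Nor does the point about half-width remove the loss of coverage, which is larger for the GMT ratio when the titre gap is wide.

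Other points narrow the scope:

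- The sizes are assumptions. The protocol's evidence concerns earlier monovalent doses, and nothing in it supports the extreme rows (98/50%, or 30- to 100-fold titre ratios) in particular.
- At the 0.8 units/ml threshold nearly everyone may be positive. At an assumed 99.5/97% the shift is only -0.125 × 2.5 = -0.3 points. The concern bears mainly on the 100 units/ml threshold and the GMT ratio.
- The T-cell sub-sample takes 10 versus 5 patients from each of the four groups, so it is 50% transplant in both arms and is not affected.
- Stratifying by group leaves other confounding in place. It removes only the component that the targets create.
- The master protocol was not supplied. Section 13.3.2 does not defer its comparison to it, whereas sections 13.3.1, 13.3.5 and 13.4 do defer their topics.

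**Conclusion.** The concern holds and should be fixed. The transplant shares of 37.5% and 25% follow exactly from the targets, and no stratification is specified in the supplied documents. If antibody response still differs between people with HIV and transplant recipients after the bivalent dose, the planned estimate is shifted on average against the Moderna vaccine, and its 95% interval covers the true within-group difference less often than stated.

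Under the assumed rates the shift is about 1 to 6 percentage points for positive response. For titres the expected GMT ratio is 0.92 to 0.75 for 2- to 10-fold titre gaps, and lower for wider gaps. If the groups no longer differ, the shift is zero and stratifying does no harm. Exploratory status keeps this from being more serious.

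**What to change.** Replace the crude comparison in section 13.3.2 with:

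- a risk difference stratified by the four recruitment groups (Mantel-Haenszel with the Sato variance, or standardised to one stated common mix);
- a GMT ratio from a linear model of log10 titre on vaccine and recruitment group;
- the same results shown by group.

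Baseline log10 titre and calendar month of vaccination belong only in sensitivity analyses, each stating how many patients it includes. For patients vaccinated before the study started, section 10.1.1 says of the baseline titre: "hence we will not have a baseline blood sample from those patients". Calendar month may overlap poorly between arms if the second arm opens late.

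The cost is a few sentences. Group is known for every participant because recruitment is capped by it, so no extra patients or visits are needed. The Mantel-Haenszel estimate is as precise as the crude one (SD 3.93 points for both at 97/70%). Standardising to the pooled mix costs a little: at an assumed 95/70% its SE is 4.6 points, against 4.5 for the crude Wald SE and 4.2 for the crude estimate's actual sampling error under fixed targets. For the GMT ratio, adjustment gains precision: at a 10-fold titre gap and SD 0.5, the SE of the log10 ratio falls from 0.092 to 0.069.

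The drawback is that intervals for single transplant groups will be wide. With 30 versus 10 patients and an assumed 70% response, the half-width is 1.96 × √(0.21/30 + 0.21/10) = 0.328, or about ±33 points. The by-group results should therefore be read as description.

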5.2 CLINICAL EVIDENCE TO DATE

In a phase 2–3 study, Moderna compared the 50-µg bivalent vaccine mRNA-1273.214 (25 µg each of ancestral Wuhan-Hu-1 and omicron B.1.1.529 [BA.1] spike messenger RNAs) with their previously authorized 50-µg mRNA-1273 booster among adults who received a two-dose (100-µg) primary series and first booster (50-µg) dose of mRNA-1273 (\geq 3 months earlier) (6). "In participants with no previous SARS-CoV-2 infection, the geometric mean titers (GMT) of neutralizing antibodies against the omicron BA.1 variant were 2372.4 (95% confidence interval [CI], 2070.6 to 2718.2) after receipt of the mRNA-1273.214 booster and 1473.5 (95% CI, 1270.8 to 1708.4) after receipt of the mRNA-1273 booster. In addition, 50-µg mRNA-1273.214 and 50-µg mRNA-1273 elicited GMT of 727.4 (95% CI, 632.8 to 836.1) and 492.1 (95% CI, 431.1 to 561.9), respectively, against omicron BA.4 and BA.5 (BA.4/5), and the mRNA-1273.214 booster also elicited higher binding antibody responses against multiple other variants (alpha, beta, gamma, and delta) than the mRNA-1273 booster. Safety and reactogenicity were similar with the two booster vaccines." (6).

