6.4 STUDY OUTCOMES

6.4.1 Immunological Outcomes

Immunological endpoints:

- The proportion of patients with a positive antibody response to SARS-CoV-2 spike (S1) protein receptor binding domain in human serum or plasma assessed by the commercial immunoassay Elecsys Anti-SARS-CoV-2 S (Elecsys S) from Roche(1) 4 weeks, 8 weeks, and 6 months after vaccination. An antibody response will be considered to be still sufficient, using the threshold ≥100 units/ml, predicting a protective immune response as indicated by Hall et al.(2), and Khoury and colleagues.(3)
- Geometric mean of quantitative antibodies against RBD at 4 weeks, 8 weeks, and 6 months using Elecsys S test from Roche.
- The proportion of patients with a positive antibody response using SARS-CoV-2 spike (S1) Elecsys S by Roche, using a threshold of ≥0.8 units/ml as defined by the manufacturer at 4 weeks, 8 weeks, and 6 months.
- T-Cell response, using a commercially available IFN-γ release assay (Quant-T-Cell SARS-CoV-2 by Euroimmun and Elecsys® IGRA SARS-CoV-2 by Roche) in a subsample of 60 patients (40 receiving bivalent (Wuhan/BA.1) SARS-CoV-2 mRNA-1273.214 vaccine by Moderna; 20 receiving bivalent (Wuhan/BA.1) SARS-CoV-2 mRNA vaccine by Pfizer-BioNTech) 4 weeks and 6 months after vaccination (sub-sample will be decreased to 40 patients in Scenario 2).

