7.4 STUDY POPULATION

This is a multi-centre study recruiting patients from 3 of the 7 study centres of the SHCS and 3 of the 6 study centres of the STCS (i.e. University Hospital Basel, University Hospital Zürich, Inselspital University Hospital Bern [only SHCS], and University Hospital Lausanne [CHUV; only STCS]). Both cohorts are representative for individuals living with HIV and solid organ transplants:

SHCS study centres:

- Department of Infectious Diseases, Inselspital University Hospital Bern, University of Bern
- Division of Infectious Diseases & Hospital Epidemiology, University Hospital Basel
- Division of Infectious Diseases and Hospital Epidemiology, University Hospital Zurich, University of Zurich

STCS study centres:

- Klinik für Pneumologie, Universitätsspital Zürich
- Klinik für Nephrologie, Universitätsspital Zürich
- Klinik für Pneumologie, Universitätsspital Basel
- Klinik für Transplantationsimmunologie & Nephrologie, Universitätsspital Basel
- Service de pneumologoie, Universitätsspital Lausanne (CHUV)
- Centre de transplantation d'organes, Universitätsspital Lausanne (CHUV)

The cohorts are described in more detail elsewhere (14, 15, 17, 18). The study will be explained to eligible patients during their visit at the cohort centre. Cohort patients will be contacted by phone or letter to inform them about the study.

Inclusion and exclusion criteria:

Inclusion criteria:

- Patients with either a HIV infection or recipients of solid organs registered in the SHCS and STCS cohorts and signed informed consent form
- Patients aged ≥18 years
- Patients receiving a new bivalent (Wuhan/Omicron BA.1) mRNA SARS-CoV-2 vaccine in the frame of clinical routine, according to the treating physician
- Provide consent for the COVERALL observational bivalent booster extension study (third subprotocol)

Exclusion criteria:

- Acute symptomatic SARS-CoV-2 infection, influenza or other acute respiratory tract infection
- Any emergency condition requiring immediate hospitalization for any condition
- Known allergy or contra-indications for vaccines or any vaccine components or any other contraindication to receive the vaccine according to the treating physician
- Patients who did not receiv the "baseic immunization" SARS-CoV-2 vaccination (e.g. two shots of Spikevax from Moderna, two shots of Comirnaty from Pfizer-BioNtech).

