10. STUDY ASSESSMENTS

Study flow chart(s) / table of study procedures and assessments

Study schedule

Assessment	Baseline	4 weeks	8 weeks	6 months
		(± 1 week)	(± 2 weeks)	(± 4 weeks)
Eligibility and consent ^a	Х			
Baseline assessment	Х			
Assessment of monoclonal antibody treatment and flu vaccination	Х	X	X	X
Vaccination (mRNA-1273.214 or product by Pfizer-BioNtech) in the frame of clinical routine ^b	Х			
Anti-SARS-CoV-2 S and N antibody tests (Elecsys® Roche)	Х	X	x	x
T-cell test (IFN-γ release assay): Quant-T-Cell SARS-CoV-2 by Euroimmun and Elecsys® IGRA SARS-CoV-2 by Roche	х	×		X
Only in sub-sample of 60 patients (Scenario 1) or 40 patients (Scenario 2)				
Clinical outcomes		Х	Х	х
Vaccine specific adverse events		Х		
Serious adverse events		Х	Х	х

^a Informed consent can also be given at later time point if bivalent vaccine was already administered in the frame of clinical routine and consent is only referring to blood samples and use of data.

^b Will be administered in the frame of clinical routine based on recommendation from treating physician

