10.1.2 Assessment of clinical endpoints

Patients are informed to contact center physicians in case an asymptomatic or symptomatic SARS-CoV-2 infections was diagnosed outside the settings of participating cohort centers. Clinical endpoints will be assessed at 4 weeks (±1 week), 8 weeks (±2 weeks) and 6 months (±4 weeks).

 Newly PCR-confirmed Covid-19 infection (identified by the presence of anti–SARS-CoV-2 nucleocapsid antibodies, or PCR or rapid antigen test)

During all visits at the trial centres (a PCR SARS-CoV-2 test will only be conducted if the treating physician would also conduct such a test during clinical routine (e.g. exposure to infected individual). PCR tests done in between independently will be recorded with dates and results. In case of a positive test result, physicians will check for symptoms and patients will be followed-up according to clinical routine and physicians' judgement.

• Newly PCR-confirmed symptomatic Covid-19 infection with at least one of the following symptoms (i.e. fever or chills, cough, shortness of breath or difficulty breathing, fatigue, muscle or body aches, headache, new loss of taste or smell, sore throat, congestion or runny nose nausea or vomiting, and diarrhea) at any time during the 48 weeks of follow-up

During all visits at the trial centres a PCR SARS-CoV-2 test will only be conducted if the treating physician would also conduct such a test during clinical routine (e.g. COVID-19 related symptoms; exposure to infected individual). In case of a positive test result, physicians will check for symptoms and patients will be followed-up according to clinical routine and physicians' judgement.

• Severe COVID-19 infection requiring hospitalization or leading to death

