11.1.2 Baseline assessment (before application of bivalent SARS-CoV-2 vaccination)

Patient will return the signed consent form which will also be signed by the treating physician. Patients will provide a blood sample of EDTA blood at the local study centre. After this they will go to the vaccination centre and receive the bivalent mRNA SARS-CoV-2 vaccine (either by Moderna or Pfizer-BioNTech) in the frame of clinical routine. Patients will also be asked about their previous vaccine history (i.e. which vaccines they received and when [months and year]) and if they have received monoclonal antibodies.

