7.1 Eligibility criteria

Inclusion and exclusion criteria as defined in the master protocol:

Inclusion criteria:

- All patients with either a chronic HIV infection or recipients of solid organs registered with informed consent from the SHCS and STCS cohorts aged ≥ 18 years
- Patients with solid organ transplantation of lungs or kidneys at least one month post-transplantation with a prednisone dose of 20mg or less.
- Additional consent for participation in the pilot trial
- Covid-19 vaccination recommended by treating physician

Exclusion criteria:

- Pregnancy
- Acute symptomatic SARS-CoV-2 infection, influenza or other acute respiratory tract infection
- Known allergy or contra-indications for vaccines or any vaccine components
- Any emergency condition requiring immediate hospitalization for any condition
- Patients with previous PCR documented SARS-CoV-2 infection and, or documented antibodies less than 3 months prior to randomisation
- Patients with solid organ transplantation (lung or kidney) with the following conditions:
 - Solid organ transplant recipients less than one month post-transplantation
 - Solid organ transplant recipients with the use of T-cell depleting agents in the last 3 months (i. e induction treatment in standard risk or high-risk immunological situation or rejection treatment).
 - Solid organ transplant recipients with the need of pulse corticosteroids (>100 mg prednisone or equivalent) in the last 1 month or rituximab in the last 6 months
 - Solid organ transplant recipients with the need of any kind of chemotherapy treatment

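### Sub-study 3 measures anti-N at baseline, but the analyses written in 13.3.2 use it in no antibody result, so any arm imbalance in prior infection enters the crude Scenario 1 contrasts

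*Protocol*

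**What the plan says.** All references are to the Protocol (third sub-protocol) unless stated.

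- **Measurement.** The schedule in section 10 lists "Anti-SARS-CoV-2 S and N antibody tests (Elecsys® Roche") at baseline, 4 weeks, 8 weeks and 6 months.
- **Stated use of anti-N.** Section 10.1.2 makes it one of the ways to identify a newly confirmed infection: "nucleocapsid antibodies, or PCR or rapid antigen test". No other use is given.
- **Antibody outcomes.** Section 6.4.1 defines two anti-S positivity thresholds and a geometric mean: "Geometric mean of quantitative antibodies against RBD at 4 weeks, 8 weeks, and 6 months using Elecsys S test from Roche". None refers to anti-N or to infection history.
- **Analysis.** Section 13.3.2 plans percentages and GMTs with confidence intervals and, for the vaccine comparison: "For scenario 1, we will additionally report mean difference in positive response and ratio of GMT between the two bivalent vaccines with 95% CI". It also promises a baseline table by vaccine, without saying that anti-N is in it.
- **Eligibility.** The only SARS-CoV-2 infection that section 7.4 excludes is a current one: "Acute symptomatic SARS-CoV-2 infection, influenza or other acute respiratory tract infection". The first sub-study, in the Combined protocol and SAP, section 7.1, also excluded "Patients with previous PCR documented SARS-CoV-2 infection and, or documented antibodies less than 3 months prior to randomisation". The third sub-protocol has no counterpart to that.
- **Allocation.** Under section 7.6, routine practice decides the vaccine. Under section 4.1, the Pfizer-BioNTech arm opens on approval. It is dropped if approval comes more than 3 months after the start, because the time difference would harm comparability.
- **Deferred.** Sections 13.3.1 (analysis populations) and 13.4 (missing data) point to the master protocol, which is not among the documents.

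**The concern.** Anti-S rises after both vaccination and infection, so an anti-S result after the booster does not show which of the two produced it. Anti-N is the marker that the protocol itself uses for infection. It will be known before the dose for everyone with a baseline sample, but the written analysis leaves it out.

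In Scenario 1 the stated aim is to compare two vaccines, and section 13 expects similar immunological outcomes. Nothing in the design balances prior infection between arms: vaccine choice follows routine practice, and one arm may be recruited up to about 3 months after the other. If the shares previously infected differ, the crude contrast carries that difference. It could create an apparent gap between equal vaccines or hide a real one. The planned 95% CI describes sampling error only and gives no warning of this.

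**Working it through.** **Plan's own figure.** There is none to reproduce. Section 13.1 gives a convenience sample with no SD, effect or power. The group counts do add up: 30 + 30 + 50 + 50 = 160 (Moderna) and 10 + 10 + 30 + 30 = 80 (Pfizer-BioNTech).

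**Inputs from the documents.** 160 and 80 participants; transplant recipients 60/160 = 37.5% and 20/80 = 25%.

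**Inputs assumed, because the documents give none.** k, the ratio of post-booster GMT in previously infected to uninfected patients (2 to 5); D, the arm difference in the share previously infected (5, 10 or 20 points); the within-stratum SD of log10 titre (0.6, with 1.0 as a check).

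**Step 1: bias in the GMT ratio.** Suppose the vaccines are equal within each infection stratum. The mean log titre in an arm with share p infected is then μ + p·log k. The arms differ by D·log k, so the expected crude GMT ratio is k^D.

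| D | k = 2 | k = 3 | k = 5 |
|---|---|---|---|
| 0 | 1.00 | 1.00 | 1.00 |
| 5 points | 1.04 | 1.06 | 1.08 |
| 10 points | 1.07 | 1.12 | 1.17 |
| 20 points | 1.15 | 1.25 | 1.38 |

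If the imbalance runs the other way, take the reciprocal: at 20 points, 0.87, 0.80 and 0.72.

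**Step 2: bias in the difference in positive response.** By the same argument it is δ·D, where δ is the difference in positivity between infected and uninfected patients. Since δ cannot exceed 1, the bias cannot exceed D, and it is small where nearly everyone responds.

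**Step 3: bias set against precision.** The crude CI factor is 10^(1.96·s·√(1/160 + 1/80)), with s² = 0.6² + 0.25·(log10 k)² if half are infected.

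- k = 3: s = 0.646, factor ×/÷1.49, log half-width 0.173. At D = 20 points the bias is 0.2 × 0.477 = 0.095, or 55% of the half-width. At 10 points it is 28%.
- k = 5: s = 0.694, factor ×/÷1.54, log half-width 0.186. At D = 20 points the bias is 0.2 × 0.699 = 0.140, or 75% of the half-width. At 10 points it is 38%.

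**Step 4: simulation** (equal vaccines, 160 vs 80, 4,000 runs per setting). The table shows how often the 95% CI for the GMT ratio excludes 1.

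| Infected, arm 1 vs arm 2 | SD | k | Crude | Adjusted for anti-N |
|---|---|---|---|---|
| 50% vs 50% | 0.6 | 3 | 5% | 5% |
| 50% vs 60% | 0.6 | 3 | 9% | 5% |
| 50% vs 60% | 0.6 | 5 | 11% | 5% |
| 50% vs 70% | 0.6 | 3 | 20% | 5% |
| 50% vs 70% | 0.6 | 5 | 32% | 5% |
| 50% vs 70% | 1.0 | 3 | 10% | 5% |
| 50% vs 70% | 1.0 | 5 | 17% | 5% |

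The adjusted ratio averaged 1.00 throughout. This is the ideal case, with anti-N known for everyone and marking infection without error.

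**Step 5: precision after adjustment.** At SD 0.6 the adjusted factor is 10^(1.96 × 0.6 × √(1/160 + 1/80)) = ×/÷1.45, slightly narrower than the crude one. Using anti-N-negative participants only (80 vs 40 if half are negative) gives ×/÷1.69.

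**Step 6: anti-N alone is not enough.** The planned transplant share differs by 12.5 points. If the HIV:transplant GMT ratio were 2, 5 or 10 (assumed), the crude Moderna:Pfizer-BioNTech ratio for equal vaccines would be R^(−0.125) = 0.92, 0.82 or 0.75. Patient group therefore belongs in the same model.

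**The case against.** **The study is exploratory.** Section 13 says so, the sample is a convenience sample, and the comparison is openly described as non-randomised, with a cap on the delay between arms. This stands, and it limits the point: no error rate or formal conclusion is broken. The contrast is still planned and will be read, and the variable that would help interpret it is already being measured.

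**The size is assumed.** This also stands. The documents give no infection prevalence by arm, no k and no SD. A reader might infer that the contrast will be biased; the documents show only that it is unprotected.

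**The master protocol may define an infection-naive population.** It may. The claim is limited to the analyses written in 13.3.2.

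Four stronger readings are tempting and not supported:

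- *The pooled GMT cannot be compared with the published one because of infection status.* Section 5.2 does quote results restricted by infection history: "In participants with no previous SARS-CoV-2 infection, the geometric mean titers (GMT) of neutralizing antibodies against the omicron BA.1 variant were 2372.4". Those are neutralising titres from a different assay in a different population. They would not be comparable with Elecsys anti-S in immunocompromised patients even after an anti-N split, and no such comparison is planned.
- *Infection history is not collected, so a new case report form item is needed.* Section 11.1.2 lists vaccine history and monoclonal antibodies ("Patients will also be asked about their previous vaccine history") and not past infection. That is a visit description, however. The case report form was not supplied, section 7.5 says the platform draws on all clinical and laboratory cohort data, and the first sub-study's schedule shows infections recorded through routine cohort follow-up.
- *The overall GMT in Scenario 2 is meaningless.* The objective is response among immunocompromised persons, and an overall GMT is a legitimate summary of that population. A split by anti-N adds to it and does not replace it.
- *Adjusting for anti-N would make the arms comparable.* It would not, given the planned transplant imbalance.

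**Conclusion.** The point holds for the text of 13.3.2. Baseline anti-N is scheduled, past infection is admitted, and no written antibody analysis uses anti-N. In Scenario 1 an arm difference in prior infection would pass straight into the crude difference and the crude GMT ratio. On assumed inputs (k = 2 to 5), the spurious ratio is 1.04–1.08 for a 5-point imbalance, 1.07–1.17 for 10 points and 1.15–1.38 for 20 points, in either direction, and 1.00 if the arms are balanced. Against a CI of about ×/÷1.5, a 5-point imbalance is minor, while a 20-point imbalance could change how the comparison is read.

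This is a weakness of interpretation in an exploratory comparison. It should be corrected because the correction is nearly free, but it does not invalidate the study. It rests on the master protocol containing no rule that already covers it.

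**What to change.** Amend 13.3.2 as follows.

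1. Keep all overall results as planned.
2. Add baseline anti-N status (negative / positive / no baseline sample) to the baseline table, by vaccine in Scenario 1.
3. Report antibody proportions and GMTs by that status as well as overall.
4. In Scenario 1, alongside the crude contrasts, report a difference in positive response and a GMT ratio adjusted for baseline anti-N status and patient group (kidney, lung, HIV with CD4 below 350, HIV with CD4 of 350 or more). For the GMT ratio this is a linear model on log titre with seven parameters: intercept, vaccine, two for anti-N, three for group. For the difference, name a method and a fallback in case nearly everyone responds in some groups.
5. Section 10.1.1 expects some participants to have no baseline blood. For them, use prior infection documented in the cohort data where available; otherwise keep them in the third level. Add a sensitivity analysis limited to participants with a baseline sample.
6. If the master protocol already defines an infection-naive set, cite it in 13.3.1.

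**Cost.** Plan wording, one extra table split and one model per contrast; no extra blood or assay. Cells will be small in the transplant groups, with only 10 kidney and 10 lung recipients planned in the Pfizer-BioNTech arm, so results by status within those groups should be descriptive. The no-sample level mixes infected and uninfected patients and keeps some confounding. Baseline status also does not deal with infections after the dose, which can raise the 8-week and 6-month anti-S results; that needs a separate rule.
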